4.3.3 Replacement of Subjects

Any subject who withdraws before completing the study but after receiving IP may be replaced at the discretion of the Sponsor and in consultation with the Investigator. Any replacement subject will be assigned to receive the same treatment as the subject he or she is replacing.

4.3.4 Study or Site Termination

Conditions may arise during the study that could prompt the study to be halted or the study site to be terminated. Conditions that may prompt such considerations include, but are not limited to, the following:

- The discovery of unexpected, serious, or unacceptable risk to the subjects enrolled in the study
- A decision on the part of Sponsor to suspend, discontinue, or shorten the study
- Study conduct at the study site may warrant termination under conditions that include the following:

- Failure of Investigator(s) to enroll eligible subjects into the study
- Failure of Investigator(s) to comply with International Conference of Harmonisation-Good Clinical Practice (ICH-GCP) guidelines, or FDA guidelines and regulations
- Submission of false information from the research facility to the Sponsor, the Clinical Monitor, the FDA, or Institutional Review Board (IRB)
- Insufficient adherence to protocol requirements
- A conflict of interest of the Investigator, his/her institution, or site personnel that would negatively impact the integrity of the clinical trial
- Institution or IRB under investigation for cause by a regulatory agency

5 INVESTIGATIONAL PRODUCT

5.1 TRL345

TRL345 is a human IgG1kappa (G1m1,17 (z,a); Km3 allotype) monoclonal antibody cloned from human B lymphocytes which targets the highly conserved AD-2, Site I epitope on the gB viral glycoprotein of the Human Cytomegalovirus (HCMV).

TRL345 is not intended to be administered as a therapeutic, i.e., antiviral agent.

5.1.1 *Packaging and Labeling*

TRL345 is manufactured, packaged, and labeled by the Sponsor's designee(s) in accordance with legal and regulatory requirements.

TRL345 is formulated as a sterile, clear, preservative-free solution and is packaged in a single-use vial for IV administration. Each vial contains 10 mL of TRL345 at 10 mg/mL.

TRL345 will be distributed to each site by the Sponsor or its designee.

The label is as follows:

5.1.2 *Storage*

TRL345 will be stored at 2°C to 8°C (36°F to 46°F).

5.2 Placebo

The placebo for this study is available 0.9% Sodium Chloride Injection USP (normal saline).

5.2.1 *Packaging and Labeling*

Commercially available 0.9% Sodium Chloride Injection USP (normal saline) in IV bags will be used. These will be provided by the Sponsor if not available at a participating study site.

5.2.2 *Storage*

Placebo should be stored at in accordance with the product label.

5.3 Preparation of Investigational Product

Preparation of the TRL345 and placebo must be performed by a designated **unblinded** site pharmacist (or otherwise qualified personnel) in accordance with the Pharmacy Manual provided by the Sponsor.

The dose of TRL345 will be determined by subject weight at the Day 1 visit. In order to maintain the blind, subjects will be dosed as follows: DG1 will receive 1 mg/kg of TRL345 or 0.1mL/kg of placebo and DG2 will receive 10 mg/kg of TRL345 or 1mL/kg of placebo. All subjects (randomized to either TRL345 or placebo) will receive IP infused over 60 minutes.

5.4 Administration of Investigational Product

IV administration of TRL345/placebo will be performed by **blinded**, trained, and qualified site personnel. A calibrated IV infusion pump will be set to deliver the total volume of IP over a 60-minute period. Start and stop times will be recorded in the subject record and eCRF.

5.5 Blinding and Unblinding

Investigators, subjects, and all study staff with direct subject contact will be blinded to treatment assignment. A designated **unblinded pharmacist** (or otherwise qualified personnel) at each site will prepare each dose. That individual should have no contact with the subjects and minimize contact with other site study personnel.

Unblinding of treatment assignment is discouraged. In the event of a medical emergency for which the identity of the treatment assignment is critical to the care of a subject, the Investigator should call the Medical Monitor to discuss. In the event that unblinding is deemed necessary, a pharmacy staff member will provide the information to the Investigator and the Medical Monitor. A decision to discontinue a subject from further IP administration is not a rationale to unblind the treatment assignment.

5.6 Investigational Product Accountability

The Investigator (or designee) will maintain an accurate record of the receipt of the IP as shipped by the Sponsor (or designee), including the date received. In addition, accurate IP disposition records will be kept, specifying the amount dispensed (vials and normal saline) to each subject and the date of dispensation.

At the completion of the study, all unused IP supplies will be returned to the Sponsor (or designee) or disposed of by the site in accordance with the Sponsor's (or designee's) written instructions.

5.7 Management of Infusion Reactions

It is required that all sites have the personnel, equipment, and medications to manage hypersensitivity reactions. Subjects must be monitored closely for signs and symptoms of an infusion reaction (IR) (e.g., fever $>38^{\circ}\text{C}$ (100.4°F), chills, flushing, bradycardia, hyper- or hypotension, itching, flushing urticaria, nausea, vomiting, abdominal pain, chest tightness, angioedema, or respiratory distress). In the event of an IR, the infusion should be slowed or stopped and restarted at the discretion of the Investigator. If a severe IR occurs (Grade 3 or 4 signs or symptoms), discontinue infusion and institute treatment as appropriate. Any infusion-related adverse event will be reported to the SMC within 24 hours.

In addition, if a subject experiences a severe IR, the following procedures will be undertaken:

- A targeted physical examination to capture medically relevant details, including but not limited to, a thorough dermatologic examination; a chest examination for breath sounds, stridor or wheezing; and a cardiac examination with attention to irregular heartbeat.
- Vital signs (sitting or supine blood pressure, heart rate, and body temperature) will be captured at the time of the IR and at least every 15 minutes until the resolution or stabilization of the IR. In addition, hematology and serum chemistry will be taken.

The Investigator may administer any medically indicated pharmacologic agent or procedure intended to relieve symptoms. Signs and symptoms of the IR and drugs given for treatment are to be recorded in the medical record and in the separate electronic case report form (eCRF) page for possible and probable IRs.

5.8 Prior and Concomitant Medications

Subjects may not receive any vaccine or booster within 14 days prior to Day 1 or planned vaccination or booster within 4 weeks after IP administration.

All prior and concomitant medications, including prescription and nonprescription medicines, will be reported in the eCRF beginning at Screening through the last study visit.

5.9 Other Study Restrictions

5.9.1 *Birth Control*

Men and WOCBP must be willing to practice a highly effective method of contraception that may include, but is not limited to, abstinence, sex only with persons of the same sex, monogamous relationship with vasectomized partner, vasectomy, hysterectomy, bilateral tubal ligation, licensed hormonal methods, or IUD for 28 days before Screening and through Day 76. Men must also refrain from donating sperm from Day 1 through Day 76.

5.10 Treatment Compliance

To ensure compliance with the dosing regimen, all doses will be administered at the investigational site by trained study personnel who have been delegated that responsibility by the Investigator.

6 STUDY PROCEDURES

Refer to [Schedule of Events](#) Table.

6.1 Definitions and Descriptions of Assessments and Procedures

Medical history – medical history will be obtained by way of subject interview and medical records. All clinically significant past and current medical history will be obtained. Clinically significant history includes those illnesses/diagnoses that are/were treated with medication for more than 14 days or other medical intervention (e.g., hospitalization, surgery, physical therapy, etc.).

Complete physical exam – examination of the following systems: ear, nose, and throat; cardiovascular; respiratory; gastrointestinal; musculoskeletal; dermatological; neurological; and confirmation of venous access.

Targeted physical exam – brief, focused examination of the subject following medical history, including assessment for AEs.

12-lead ECG – after a subject has been supine for 5 minutes, triplicate ECGs will be obtained over 5 minutes. The investigator will interpret the ECG using 1 of the following categories: normal, abnormal but not clinically significant (NCS), or abnormal and clinically significant (CS). QTcF will also be determined. Subjects may not use tobacco or nicotine within 4 hours prior to the ECG.

Vital Signs – temperature, heart rate, blood pressure. Heart rate and blood pressure should be obtained after subject is resting for 5 minutes. Height will be obtained at Screening only. Weight will be obtained at Screening, on Day 1, and at Day 43.

Serum chemistry – sodium, potassium, chloride, carbon dioxide (CO₂), urea nitrogen (BUN), creatinine (CREA), calcium, glucose, total protein, albumin, total bilirubin, alkaline phosphatase, aspartate aminotransferase (AST), alanine aminotransferase (ALT). HsCRP and LDH will be assessed at Days 1, 15, and 29 only.

Hematology – hemoglobin, red blood cell count, white blood cell count with differential, platelet count.

Hemoglobin A1c – whole blood sample at Screening

Additional safety assessments – amylase, lipase, creatine kinase, NT-proBNP, IL-1 α , fasting glucose, fasting blood insulin. Subjects must refrain from strenuous exercise within 5 days prior to assessment of creatine kinase.

CMV serology – an established ELISA assay available in commercial laboratories to detect IgG antibodies against CMV will be used to determine serostatus of subjects.

Urine drug test – amphetamines (includes methamphetamines and ecstasy/methylenedioxymethamphetamine), barbiturates, benzodiazepines, cannabinoids, cocaine

metabolites, cotinine, ethyl alcohol, methadone, methamphetamines, opiates (including heroin, codeine, and oxycodone/oxymorphone)

Women of childbearing potential (WOCBP) – not surgically sterile or post-menopausal defined as age > 40 years without menses for ≥ 2 years without an alternative medical cause for amenorrhea.

AEs, SAEs – refer to [Section 7.2](#).

Infusion reaction (IR) – refer to [Section 5.7](#).

6.2 Screening

At the time of screening, each subject will be assigned a sequential subject identification number (Subject ID).

The following assessments and procedures will be performed:

Written informed consent

Verification of eligibility

Demographics

Medical/Disease history, including review of concomitant medications

Complete physical exam, including, an assessment of venous access

Vital signs including height, and weight

12-lead ECGs in triplicate (subjects may not use tobacco or nicotine within 4 hours prior to the ECG)

Laboratory Evaluations, including:

- Serum chemistry
- Hematology
- Fasting glucose
- HbA1c
- CMV serology
- Serum pregnancy test in WOCBP
- Serology for HIV, hepatitis B and C
- Urine drug test

Schedule Day 1 visit

6.3 Randomization

Subjects who meet all inclusion and no exclusion criteria, will be sequentially enrolled into the study, assigned to DG, and randomized to receive TRL345 or placebo. Each DG will include 8 subjects (6 will be randomized to TRL345 and 2 to placebo).

Randomization code numbers will be allocated to subjects after assessment of eligibility. The randomization list will be generated by a standard software program and the randomization process will be conducted in accordance with the Standard Operating Procedures (SOPs) of the Clinical Research Organization (CRO).

6.4 On-Study Procedures

6.4.1 Study Day 1

The following procedures will be performed prior to administration of IP:

Reconfirm eligibility

Targeted physical exam

Concomitant medication assessment

Laboratory Evaluations, including:

- Serum chemistry (including hsCRP and LDH)
- Hematology
- Amylase, lipase, and creatine kinase (subjects must refrain from strenuous exercise within 5 days prior to assessment of creatine kinase)
- Fasting glucose
- Fasting blood insulin level
- NT-proBNP and IL-1 α
- Serum for PK, PD, ADA, and possible exploratory analyses (see additional times below for PK and PD)

The following procedures will be performed at the times specified below:

Vital signs within 60 minutes prior to dosing and then at 15, 30, and 60 minutes (end of the infusion), and 1 and 4 hours after the end of the infusion

Serum for PK will be obtained at prior to the start of infusion and then at end of infusion (60 minutes), and 2, 4, 6, 12, 24 (Day 2), and 48 hours (Day 3) after the start of the infusion

Serum for PD will be obtained at prior to start of infusion and then at end of infusion (60 minutes)

12-lead ECGs in triplicate within 4 hours post-completion of infusion (subjects may not use tobacco or nicotine within 4 hours prior to the ECG)

Additionally, the following will be performed:

Randomization of the subject to study/DG

Intravenous dosing of study IP per randomization assignment. A calibrated IV infusion pump will be set to deliver the total volume of IP over a 60-minute period.

Adverse events will be assessed during and after the infusion.

6.4.2 Study Days 2 and 3

The following procedures will be performed:

Targeted physical exam

Vital signs

Laboratory Evaluations, including:

- Serum chemistry
- Hematology
- Amylase, lipase, and creatine kinase (subjects must refrain from strenuous exercise within 5 days prior to assessment of creatine kinase) (Day 3 only)

- Fasting glucose (Day 3 only)
- Fasting blood insulin level (Day 3 only)
- Additional serum sample for possible exploratory analyses (Day 3 only)
- NT-proBNP and IL-1 α (Day 3 only)
- Serum for PK

AE assessment

Concomitant medication assessment

6.4.3 Study Day 8 (± 1 day)

The following procedures will be performed:

Targeted physical exam

Vital signs

Laboratory Evaluations:

- Serum chemistry
- Hematology
- Amylase, lipase, and creatine kinase (subjects must refrain from strenuous exercise within 5 days prior to assessment of creatine kinase)
- Fasting glucose
- Fasting blood insulin level
- Serum for PK, ADA, and possible exploratory analyses (ADA to be held for exploratory analysis, if warranted)

12-lead ECGs in triplicate (subjects may not use tobacco or nicotine within 4 hours prior to the ECG)

AE assessment

Concomitant medication assessment

6.4.4 Study Days 15 (± 2 days) and 29 (± 3 days)

The following procedures will be performed:

Targeted physical exam

Vital signs

Laboratory Evaluations:

- Serum chemistry (including hsCRP and LDH)
- Hematology
- Amylase, lipase, and creatine kinase (subjects must refrain from strenuous exercise within 5 days prior to assessment of creatine kinase) (Day 15 only)
- Fasting glucose
- Fasting blood insulin level
- NT-proBNP and IL-1 α

- Serum for PK, PD, ADA, and possible exploratory analyses (ADA at Day 29 to be held for exploratory analysis, if warranted)

AE assessment

Concomitant medication assessment

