Safety: Frequencies and percentages of subjects with AEs and SAEs will be summarized by dose group. Vital signs, ECGs, laboratory evaluations, and physical examination findings will be summarized with descriptive statistics by dose group. Additional serum samples will be taken and stored for possible exploratory analyses that may be necessary to further explore any unexpected safety or tolerability observations.

PK: Individual subject TRL345 serum concentrations and derived PK parameters will be summarized using descriptive statistics.

Immunogenicity: Anti-TRL345 antibodies will be summarized with descriptive statistics by DG.

PD: Serum samples will be taken and evaluated for *ex vivo* PD assessments.

SCHEDULE OF EVENTS

Study Day	Screening	1	2	3	8	15	29	43	76
Study Week					1	2	4	6	11
Window (days)	-8 (+/-6)	-1	0	0	± 1	± 3	± 3	± 3	± 5
Visit Type	A	RU	RU	RU	A	A	A	A	A
Procedure									
Informed Consent	X								
Eligibility	X	X ¹							
Demographics	X								
Medical/Disease History	X								
Complete Physical Exam	X								
Targeted Physical Exam		X ¹	X	X	X	X	X	X	
Vital Signs ²	X	X ³	X	X	X	X	X	X	
Weight	X	X ¹						X	
Height	X								
12-Lead ECG in triplicate ⁴	X	X			X				
Laboratory Tests									
Serum Chemistry ⁵	X	X ¹	X	X	X	X	X	X	
Hematology	X	X ¹	X	X	X	X	X	X	
Amylase, lipase, creatine kinase ⁶		X ¹		X	X	X			
Fasting glucose	X	X ¹		X	X	X	X	X	
HbA1C	X								
Fasting blood insulin level		X ¹		X	X	X	X	X	
Additional serum sample for possible exploratory analyses ⁷		X ¹		X	X	X	X	X	
NT-proBNP, IL-1 α		X ¹		X		X	X	X	
CMV Serology ⁸	X								
Serum Pregnancy Test (WOCBP)	X							X	
HIV, Hepatitis B, C Serology	X								
Urine Drug Test	X								
Randomization		X ¹							
Dosing of IP (TRL345 or placebo)		X							
PK sampling – serum ⁹		X	X	X	X	X	X	X	X
PD sampling – serum ¹⁰		X				X	X	X	X
ADA sampling – serum ¹¹		X ¹			X		X	X	X
Adverse Events		X	X	X	X	X	X	X	X
Concomitant Medications		X ¹	X	X	X	X	X	X	X
Overall Status								X	X

Visit Type: A = ambulant, RU = Research Unit, NA = phone call

- To be performed prior to the administration of IP.
- Vital signs include temperature, blood pressure, and heart rate. Vital signs should be obtained after subject is resting for 5 minutes. The window for all vital signs is ± 10 minutes.
- On Day 1, vital signs will be obtained within 60 minutes prior to dosing, at 15, 30, and 60 minutes (end of the infusion), and 1 hour and 4 hours after the end of the infusion.

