Consistent TRL345-specific staining (staining of 1 or more samples at 5 and 50 µg/mL) was observed in the cytoplasm, cell membrane and/or nuclei of colonic epithelium (3/3); small intestine epithelium (2/3); intercalated discs of heart myocytes (1/3 at 5 µg/mL; 3/3 at 50 µg/mL); adult liver bile duct epithelium (2/3); adult pancreas duct epithelium (2/3); epidermal keratinocytes, follicular and/or sebaceous gland epithelium, and/or superficial keratin in skin (3/3); cervix epithelium (1/3); bile duct epithelium of neonatal liver (1/3); and in duct epithelium and/or acinar cells of neonatal pancreas (2/2 at 50 µg/mL, 1/2 at 5 µg/mL).

Less consistent staining (1 or more samples at 50 µg/mL only) included cytoplasmic and/or nuclear staining in the granular cell layer of the cerebellum (3/3); corneal epithelium of the eye (2/3); epithelium, smooth muscle and/or fibromuscular cells of the Fallopian tube (3/3); epithelium, particularly gastric pits, smooth muscle cells of the muscularis externa, and submucosal vessels of the stomach (3/3); interstitial spindle cells and tubular epithelium in the kidney (1/3); placental villous mesoderm and endothelium (1/3); and connective tissue stromal cells in the prostate (1/3). Much of this inconsistent staining may be non-specific even though similar staining was not observed in matched negative controls. Staining in tissues with only 1 sample weakly positive at 50 µg/mL only (kidney, placenta, and prostate) is likely to be non-specific and not physiologically relevant.

Non-specific staining in several tissues confused interpretation of possible concurrent specific staining. These tissues included: liver (adult and neonatal), pancreas (adult and neonatal), salivary gland, pituitary, stomach, and skin.

Due to the widespread prevalence of chronic HCMV infection in humans, the observed sporadic binding is presumed to have been due to latent HCMV infections. That is, latent HCMV infection includes slow but persistent replication of the virus [Traylen 2011].

- **Homology of HCMV gB and TRL345 Binding Epitope within Human Proteome**

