To further explore the possibility that TRL345 binds human proteins, an immuno-affinity extraction study was conducted. After extracting solubilized human proteins on a sorbent to which TRL345 was conjugated, the eluted proteins were analyzed by mass spectroscopy. Low homology to the TRL345 binding epitope among the eluted proteins was noted in 7 of the 54 unique skeletal muscle proteins (non-staining tissue by immunohistochemistry), 18 of the 197 unique pancreas proteins (positive staining) and 6 of the 414 proteins that were common to both the skeletal muscle and pancreas. The majority of the hit proteins are primarily intracellular. Homology to the TRL345 epitope was minimal for all of these, and none of them matched the tissue distribution of the staining observed in the TCR study.

Moreover, the toxicity study in rats did not reveal any toxicity signals for the gastrointestinal tissues in which binding in the human tissue cross reactivity study was observed. There were no signs of edema, no increase in inflammatory cells, and no abnormalities in clinical and hematology. The sparse binding of TRL345 in the pancreas tissue by immunohistology was only observed with the exocrine tissue (98% of the organ); no binding was observed to beta-cells (insulin producing cells).

The possibility of adverse off-target binding cannot be excluded. The main risk of adverse off-target binding is to the gastrointestinal tissues and pancreas, and includes the possibility of diarrhea, abdominal spasms and discomfort.

1.3.2 *Pharmacokinetics*

TRL345, administered as a single bolus IV injection at 10 mg/mL, was well tolerated in Sprague-Dawley rats. T_{max} occurred 5 minutes after the end of dosing and the C_{max} was 184 $\mu\text{g/mL}$. The elimination curve, accurately described by an open two compartment pharmacokinetic model, showed a short distribution phase with a $t_{1/2\alpha}$ of 3 hours and a longer elimination phase with a $t_{1/2\beta}$ of 46 hours. The volume of distribution (V_d) was approximately equivalent to plasma volume (60 mL/kg); however, the volume of distribution at steady state (V_{ss}), 305 mL/kg, indicated some distribution into the extravascular space. $AUC_{0-\infty}$ was 1,642 $\mu\text{g}\cdot\text{hr/mL}$. These data are consistent with other monoclonal antibodies and do not suggest that TRL345 accumulates in a specific tissue or that there is an “antibody sink.”

1.3.3 *Toxicology*

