6.4.5 Study Day 43 (± 3 days) or Early Termination

The following procedures will be performed:

Targeted physical exam

Vital signs including weight

Laboratory Evaluations:

- Serum chemistry
- Hematology
- Fasting glucose
- Fasting blood insulin level
- NT-proBNP and IL-1 α
- Serum for PK, PD, ADA, and possible exploratory analyses
- Serum pregnancy test in WOCBP

AE assessment

Concomitant medication assessment

Overall status

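### Amylase and lipase stop at Day 15 and are not tested at early termination, so at 10 mg/kg a late symptomless rise could go undetected although the pancreas is a named off-target risk

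*Protocol*

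**What the plan says.** The Schedule of Events row "Amylase, lipase, creatine kinase" has marks at Day 1 (predose) and Days 3, 8 and 15, and none later. Protocol section 6.4 agrees. The list shared by Days 15 and 29 in 6.4.4 limits the tests to the earlier visit: "Amylase, lipase, and creatine kinase (subjects must refrain from strenuous exercise within 5 days prior to assessment of creatine kinase) (Day 15 only".

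Section 6.4.5 serves both Day 43 and early termination. It includes fasting glucose and "Fasting blood insulin level", but neither amylase nor lipase. Routine chemistry does not fill the gap. Section 6.1 defines it as "Serum chemistry – sodium, potassium, chloride, carbon dioxide (CO₂), urea nitrogen (BUN), creatinine (CREA), calcium, glucose, total protein, albumin, total bilirubin, alkaline phosphatase", followed by AST and ALT, with hsCRP and LDH at Days 1, 15 and 29 only.

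On risk, section 1.3.1 says: "The main risk of adverse off-target binding is to the gastrointestinal tissues and pancreas". It places the sparse pancreatic binding in exocrine tissue and adds that "no binding was observed to beta-cells (insulin producing cells". The tissue study applied TRL345 at 5.0 and 50.0 µg/mL. The entry "adult pancreas duct epithelium (2/3" stands in the group defined by staining of at least one sample at both concentrations.

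**The concern.** The monitoring does not follow the stated risk. The compartment that stained is exocrine, but the exocrine markers end at Day 15 and the endocrine markers run four weeks longer. Neither document gives a reason.

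The Day 15 committee review before escalation explains why the enzymes are measured by then. It does not explain stopping there: glucose, insulin, NT-proBNP and IL-1α continue to Day 43, and the 10 mg/kg group has no later escalation.

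Safety is the primary objective, and one exploratory objective looks for off-target binding in adverse events, clinical labs and PK. Direct enzyme evidence would end at Day 15, leaving 76 − 15 = 61 days of follow-up without it. A subject who terminates early, at any time, has no scheduled enzyme test at exit.

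**Working it through.** The documents give no human concentration in text (the predicted human curves are in a figure that is not shown), so there is no plan figure to reproduce. The check asks whether serum levels after Day 15 could plausibly still exceed a concentration that stained pancreas.

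**Inputs from the protocol:** doses of 1 and 10 mg/kg (3.3); staining concentrations of 5 and 50 µg/mL (1.3.1); rat initial volume 60 mL/kg, rat Vss 305 mL/kg and rat elimination half-life 46 hours (1.3.2).

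**Assumptions:** one compartment; human volume V 60–100 mL/kg; half-life 14–28 days. Sensitivity cases use a 7-day half-life, the rat Vss and the rat half-life.

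**Formula:** C(day) = (Dose/V) × 2^(−(day − 1)/t½).

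At 10 mg/kg, C0 is 10/0.100 = 100 µg/mL to 10/0.060 = 166.7 µg/mL.
- Day 29, low end: 100 × 2^(−28/14) = 25. High end: 166.7 × 2^(−28/28) = 83.
- Day 43, low end: 100 × 2^(−42/14) = 12.5. High end: 166.7 × 2^(−42/28) = 59.

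| Dose and assumptions | Day 15 | Day 29 | Day 43 |
|---|---|---|---|
| 10 mg/kg, V 60–100, t½ 14–28 d | 50–118 | 25–83 | 12.5–59 |
| 10 mg/kg, V 60–100, t½ 7 d | 25–42 | 6–10 | 1.6–2.6 |
| 10 mg/kg, V 305, t½ 14–28 d | 16–23 | 8–16 | 4–12 |
| 1 mg/kg, V 60–100, t½ 14–28 d | 5.0–11.8 | 2.5–8.3 | 1.25–5.9 |

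(µg/mL; V in mL/kg)

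**Half-life needed to stay above 5 µg/mL:** t½ = ln 2 × (day − 1)/ln(C0/5). At 10 mg/kg:
- V 60–100: about 2.8–3.2 days at Day 15, 5.5–6.5 at Day 29 and 8.3–9.7 at Day 43.
- V 305 (C0 = 32.8): about 5.2 days at Day 15, 10.3 at Day 29 and 15.5 at Day 43.

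**Where the overlap fails:**
- With V 305 and a half-life below about 5 days, the 10 mg/kg level is already under 5 µg/mL at Day 15.
- With the rat half-life it is about 1 µg/mL or less at Day 15.
- At 1 mg/kg with V 305, C0 is 1/0.305 = 3.3 µg/mL, so 5 µg/mL is never reached.
- Against 50 µg/mL with V 60–100, the 10 mg/kg level stays above at Day 29 only if the half-life is at least about 16–28 days.

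The early-termination gap rests on no kinetic assumption. It follows from the list in 6.4.5.

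**The case against.** A reader might infer that late pancreatic injury would be missed and that only symptoms could reveal it. The documents do not support that.
- Adverse events are recorded to Day 76 and followed to resolution or stabilization, and 7.3 provides for further tests when clinically indicated.
- The harm described in 1.3.1 is largely symptomatic.
- Physical examination and chemistry continue to Day 43, hsCRP and LDH to Day 29, and IL-1α to Day 43. These are less specific than lipase but not uninformative.
- A subject who left on Day 5 would have had enzymes on Day 3, and any abdominal symptoms would be followed as an adverse event.

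A reader might also take the pancreas to be a named organ of the primary objective or of the off-target endpoint. It is neither. Section 2.2.5 lists gastrointestinal and CNS events, LDH, hsCRP, IL-1α, AUC and half-life. The pancreas appears as a risk in the nonclinical text.

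The staining itself is uncertain. Section 1.3.1 says non-specific staining confused interpretation in pancreas, presumes latent HCMV as the cause of the sporadic binding, and reports no gastrointestinal toxicity signal in rats. A serum level above a cryosection staining concentration is not tissue injury. The rat data were also two-compartment, so putting the whole dose in 60–100 mL/kg probably gives high values.

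All of this stands and limits the point. One safeguard does not close the gap. Serum stored on Days 29 and 43 may be used for extra safety testing (6.5), but its use is optional and tied to unexpected observations. A silent, unmeasured enzyme rise would prompt none. The same section says stored samples stay anonymized, which may hinder linking a result to a subject.

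**Conclusion.** The point holds in limited form, as a cheap improvement in detection. The schedule is internally consistent; what is unexplained is the mismatch with the protocol's own risk statement. At 10 mg/kg, and only under assumed antibody-like kinetics, levels at Days 29 and 43 would exceed the lower staining concentration. At 1 mg/kg this depends on the assumed half-life and volume, or fails. It is also wrong to infer that Day 15 would suffice only if the human half-life were close to the rat's 46 hours, since the rat Vss with anything below about 5 days gives the same result.

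The consequence is that a late asymptomatic enzyme rise could go undetected prospectively, and that early termination has no closing enzyme test at either dose. The calculation shows plausibility, not a late hazard.

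**What to change.** Add amylase and lipase to the chemistry samples already drawn at Day 29 and at Day 43/Early Termination, in the Schedule of Events and in 6.4.4 and 6.4.5. Exocrine markers would then run as long as fasting glucose and insulin, and the stretch to Day 76 without an enzyme test would fall from 61 to 76 − 43 = 33 days. If the sponsor prefers to stop at Day 15, the protocol should say why. The time-point table in SAP section 8.5 names neither test, so both should be added there.

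Cost: a schedule amendment and two analytes at up to 2 visits × 16 subjects = 32 results each, with no extra visit or blood draw. The downside is a few incidental mild elevations to follow up.
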